9.10. Sensitivity and supportive analyses

Sensitivity analyses will be limited to the primary outcome and will consist of:

- Per-protocol analysis; this will comprise the adherent population as described in sections 5.4;
- No interaction of treatment effect (as a result of the two trial allocations) is assumed. To explore this assumption, a treatment group interaction parameter (randomisation 1 by randomisation 2) will be added to the base model for trial comparisons A and B only as comparisons C-E only include one of the randomisations[4.13]). A p-value for this interaction parameter will be produced and examined as well as the interaction coefficient and 95% CI. If this parameter is significant, then treatment effect estimates within randomisation 2 allocation (for randomisation 1) and randomisation 1 allocation (for randomisation 2) will be explored as per the subgroup analysis methods described in section 9.9. It should be acknowledged that any test for interaction will be underpowered to detect a significant effect.
- An analysis to assess the effect of missing responses for the primary outcome only. Unadjusted models will be utilised. This analysis will explore the possibility that missing

responses are 'missing not at random' (MNAR) using a tipping point approach. In this analysis, for women with missing outcome data, events will be added sequentially in each of the groups in turn to determine the point where the general conclusion changes (for example from positive to inconclusive in terms of the CI). An assessment can then be made about whether the event rate in the missing responses between groups is likely to be plausible when compared with the event rate in the non-missing data. Two scenarios will be considered as follows:

- Scenario A: In the 'treatment A' group, assume all missing responses are nonevents (i.e. women randomised who experience a live birth is no). For missing responses in the 'treatment B' group, we will first replace X missing responses with events (i.e. X additional cases of live birth) where X is the number of events such that the event rate in the missing responses is equal to the event rate in the non-missing responses in the 'treatment B' group. This will be regarded as the base case. All other missing responses in the 'treatment B' group will be considered as non-events. An unadjusted model will be fitted. Event rates will be compared between groups. The CI from the treatment estimate (from the RR of the log-binomial model) will be examined and stored. Following the base case, an additional event will be added to the 'treatment B' group and the above procedure repeated (unadjusted model fitted and the RR and CI examined). This process will end when the number of events added to the 'treatment B' group are equal to the original number of missing responses in this group. The tipping point for the 'treatment B' group will occur when enough events have been added such that the upper/lower limit of the CI from the corresponding model differs from that of the primary ITT finding (in regards to whether the CI crosses the null value of one).
- Scenario B: In the 'treatment B' group, assume all missing responses are nonevents (i.e. women randomised who experience a live birth is no). For missing responses in the 'treatment A' group, we will first replace X missing responses with events (i.e. X additional cases of live birth) where X is the number of events such that the event rate in the missing responses is equal to the event rate in the non-missing responses in the 'treatment A' group. This will be regarded as the base case. All other missing responses in the 'treatment A' group will be considered as non-events. An unadjusted model will be fitted. Event rates will be compared between groups. The CI from the treatment estimate (from the RR of the log-binomial model) will be examined and stored. Following the base case, an additional event will be added to the 'treatment A' group and the above procedure repeated (unadjusted model fitted and the RR and CI examined). This process will end when the number of events added to the 'treatment A' group are equal to the original number of missing responses in this group. The tipping point for the 'treatment A' will occur when enough events have been added such that the upper/lower limit of the CI from the corresponding model differs from that of

the primary ITT finding (in regards to whether the CI crosses the null value of one).

10. Analysis of sub-randomisations

Not applicable.

11. Health economic analysis

As indicated in the protocol there will also be an economic analysis. The details of this analysis are documented separately.

12. Statistical software

Statistical analysis will be undertaken in the following statistical software packages: SAS software and Stata.

13. References

1. Huque MFD, A. ; D'Agostino, R. Multiplicity Issues in Clinical Trials With Multiple Objectives. Statistics in Biopharmaceutical Research 2013;5.Gupta SK. Intention-to-treat concept: A review. Perspect Clin Res. 2011;2(3):109-112.

2. Gupta SK. Intention-to-treat concept: A review. Perspect Clin Res. 2011;2(3):109-112.

5. Zou G. A modified Poisson regression approach to prospective studies with binary data. Am J Epidemiol. 2004;159(7):702-6.

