Following review by the funder (NIHR HTA) and due to the impact of the COVID-19 pandemic on participant accrual, the sample size target was revised on 3 February 2023 to aim for at least 80% power within the letrozole plus metformin vs clomifene plus metformin comparison, rather than the 90% power originally described. 800 participants (with primary outcome data gained on 760) within this comparison would provide 81% power (p=0.05) to detect a difference of 10% between groups (the same assumptions of 44% and 34% in the two groups as previously stated).

Due to the factorial design, this agreement would mean a sample of 1600 participants (with primary outcome data gained on 1520 assuming 5% loss to follow-up) within the two main comparisons (letrozole vs clomifene and metformin vs placebo). This number of participants would provide 98.5% power (at p=0.05) to detect a difference of 10% between groups (the same assumption of 39% vs 29% in both comparisons as previously stated).

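### The tipping-point analysis in SAP 9.10 starts far from missing-at-random and judges unadjusted models against the adjusted primary result, so for borderline results it can tip at its first point or because the model changed

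*SAP*

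**What the plan says.** SAP 9.3 analyses received data only and relies on a sensitivity analysis of the primary outcome to show what missing data could do. SAP 9.10 describes that analysis as a tipping-point exploration of outcomes missing not at random.

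- **Fixed arm.** Scenario A takes treatment A and says to "assume all missing responses are nonevents". Scenario B does the same for treatment B. Within a scenario this arm never leaves zero.
- **Varied arm.** The other arm's missing outcomes start at that arm's observed event rate (the base case). Events are then added one at a time until every missing outcome is a birth. The steps never go below the observed rate.
- **Model.** "Unadjusted models will be utilised" for these runs. SAP 9.1 and 9.5 give the primary result from a mixed-effects binomial model adjusted for the minimisation variables, with centre as a random intercept.
- **Tip.** A tip is declared when the interval's position relative to 1 "differs from that of the primary ITT finding".
- **Interpretation.** The plausibility of the event rates among the missing is then assessed against the rates in the observed data.

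No unadjusted complete-case result is planned as a reference.

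**The concern.** A tipping-point analysis should show how far the missing outcomes must depart from the observed pattern before the conclusion changes. Two features of the stated rule work against that.

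First, the starting point is already strongly differential. At the design rates it compares 0% births among one arm's missing women with about 34% among the other's (comparison C), or 0% with about 29% (comparisons A and B). If the result has tipped there, the steps move further out. The crossing lies behind the start and is not found.

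Second, the tipping runs and the reference result come from different models. If the adjusted interval excludes 1 and the unadjusted one does not, a tip is recorded that has nothing to do with missing data.

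At stake is the reading of the SAP's only missing-data analysis, in the borderline results where readers will lean on it most.

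**Working it through.** **Inputs (SAP 4.7).** Comparison C: 800 randomised and 760 with outcome, which "would provide 81% power (p=0.05) to detect a difference of 10% between groups", with "the same assumptions of 44% and 34% in the two groups as previously stated". Comparisons A and B: 1600 randomised, "with primary outcome data gained on 1520 assuming 5% loss to follow-up", rates 39% and 29%, stated power 98.5%.

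**Assumptions.** Losses are equal by arm: 380 observed and 20 missing per arm in C, 760 and 40 in A and B. Treatment A is the letrozole arm in C and the better arm in the other examples. The starting number of events is rounded to the nearest integer.

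**Reproducing the plan's power.** Two-sided 0.05, pooled variance under the null:

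z = [d√n − 1.96√(2p̄(1−p̄))] / √(p₁(1−p₁) + p₂(1−p₂))

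- C: (0.10√380 − 1.96√0.4758)/√0.4708 = 0.87, power 80.8% (stated 81%).
- A and B: (0.10√760 − 1.96√0.4488)/√0.4438 = 2.17, power 98.5% (as stated).

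**Tipping steps.** With a/n₁ and b/n₂ births, RR = (a/n₁)/(b/n₂), SE(log RR) = √(1/a − 1/n₁ + 1/b − 1/n₂), and the 95% CI is RR·exp(±1.96·SE). The base-case number in the clomifene arm is 20 × 129/380 = 6.8, so 7.

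Borderline example in C, observed 160/380 (42%) versus 129/380 (34%). All rows are unadjusted, so the change of model plays no part here.

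| Births among the missing, letrozole vs clomifene | Totals | RR (95% CI) |
|---|---|---|
| Complete case | 160/380 vs 129/380 | 1.24 (1.033 to 1.490) |
| Both at observed rates, 8/20 vs 7/20 | 168/400 vs 136/400 | 1.24 (1.033 to 1.477) |
| Scenario A base case, 0/20 vs 7/20 | 160/400 vs 136/400 | 1.18 (0.981 to 1.411) |
| Not run: 0/20 vs 4/20 | 160/400 vs 133/400 | 1.20 (1.001 to 1.445) |
| Not run: 0/20 vs 5/20 | 160/400 vs 134/400 | 1.19 (0.994 to 1.434) |
| Scenario B base case, 8/20 vs 0/20 | 168/400 vs 129/400 | 1.30 (1.08 to 1.56) |

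Scenario A has tipped at its first point, and the crossing (5/20) is below its start (7/20). With letrozole held at 8/20, the lower limit is 1.006 at 11/20 in the clomifene arm and 0.9994 at 12/20. The tip then needs 60% births among that arm's missing women, against 34% observed. The plan does not produce this statement.

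**Range affected.** In C, with 129/380 in the control arm, every significant result from 156 to 162 births (7.1 to 8.7 points) tips at the base case. In A and B, with 220/760 and a base case of 12/40, this holds from 256 to 268 births (4.7 to 6.3 points). None of these tips with both arms at their observed rates.

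**At the design rates.**
- C, 167/380 vs 129/380: the base case is 1.23 (1.03 to 1.47), not tipped. With 0/20 in the letrozole arm, the lower limit is 1.006 at 10/20, 0.9996 at 11/20 and 0.993 at 12/20, so the tip is at 11/20.
- A and B, 296/760 vs 220/760: the base case is 1.28 (1.11 to 1.47). The tip comes at 39/40 (lower limit 0.9986).

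**How often.** Share of significant results that tip at the first point (200,000 simulated trials per setting, unadjusted):

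| Setting | 2% missing | 5% missing | 10% missing |
|---|---|---|---|
| C, 44% vs 34% | 9% | 23% | 52% |
| C, 41% vs 34% | – | 40% | – |
| A/B, 39% vs 29% | – | 6% | 24% |
| A/B, 34% vs 29% | – | 46% | – |

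With no true effect and 5% missing, 10% (C) to 15% (A/B) of non-significant results become significant at a base case.

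**Change of model.** A separate simulation had no missing data and compared adjusted with unadjusted verdicts (modified Poisson, 1,500 trials per setting). Between 3% and 8% of adjusted-significant results were not significant unadjusted. This rests on assumed covariate effects, which the documents do not give, so it shows only that the problem can occur.

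**The case against.** The strongest reply is that the plan is more informative than it looks, and much of that reply stands.

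- A reader might infer that missing-at-random is never examined. The documents do not support this. The primary analysis on received data with covariate adjustment already makes essentially that assumption, and the complete-case and both-at-observed-rates rows above nearly coincide. SAP 9.10 is explicitly about departures from it.
- A reader might infer that all mild departures are ignored. If the base case does not tip, it bounds every milder departure in the same direction, because the lower limit falls steadily as births are removed from the better arm or added to the other. The gap is confined to results that tip at once.
- A reader might object that one scenario moves away from the null. That is no defect. The hypothesis in SAP 4.8 is two-sided, and the mirror pair covers either direction and a null result.
- The 42% versus 34% example is borderline, below the planned 10 points. At the design rates the procedure gives interpretable answers.
- The SAP calls 5% attrition a worst case, and the protocol expects little missing data. With 8 missing per arm (165/392 vs 133/392), the base case is 1.21 (1.01 to 1.45) and the tip comes at 6/8.
- The plausibility step lets the team discount a tip at 0% versus 34%. It can judge only the points that were run, however, and cannot supply a crossing below the start.

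Protocol 13.2.4 mentions multiple imputation, which SAP 9.10 does not include. That is a separate matter. The protocol supplied is version 1.0 of 2019, and the SAP's eligibility criteria and sample size already differ from it, so a later version may exist. No contradiction should be inferred from this.

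**Conclusion.** The point holds in a limited form. The rule in SAP 9.10 can tip at its first point without showing where the crossing lies, and it can record a change of model as a missing-data tip. The first problem affects mainly borderline results, or loss of about 5% or more: roughly 23% of significant results in comparison C and 6% in A and B under the design effects with 5% missing. These shares assume equal loss by arm and unadjusted Wald intervals. The second problem follows directly from the wording, but its frequency cannot be derived from the documents.

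Where the base case does not tip, the procedure is informative, and the plausibility step partly mitigates the rest. It would be wrong to conclude that the primary result is at risk: the primary estimate and test are unchanged.

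**What to change.** In SAP 9.10:

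1. Report the unadjusted complete-case RR and CI for each comparison, and define tipping against that result, so that reference and tipping runs share one model.
2. Extend Scenarios A and B to a two-way grid of 0 to m events among the m missing outcomes in each arm. Mark the point where both arms follow their observed rates, and the contour where the CI reaches 1. The grid contains every point now planned, so nothing is lost.
3. Keep the plausibility assessment and apply it to the contour.

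The cost is a few sentences of SAP text, a double loop in the code and one extra figure or table. No new data are needed. Delta-adjusted multiple imputation with the primary model would be an optional alternative; this point does not require it.

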Appendix A: Deviations from SAP

This report below follows the statistical analysis plan dated *<insert effective date of latest SAP>* apart from following:

Reason
<insert, analyses="" by="" e.g.="" exploratory="" request="" tmg=""></insert,>

Appendix C: Schedule of assessments

			From randomisation							
Visit	Screening before clinic	Baseline clinic	Month 1	Month 2	Month 3	Month 4	Month 5	Month 6	Month 4-9*	Month 2-18**
Eligibility check	х	х								
Valid informed consent		х								
Relevant medical history taken	x	х								
Concomitant medication		х	х	x	х	х	х	х	х	х
Randomisation		х								
Routine blood tests	x	х								
D21 progesterone concentration blood test (where applicable)			x	x	x	x	x	x		
Dispensing of IMP		х								
Ultrasound monitoring of ovulation (optional, depending on local practice)			x							
Drug returns (participant visit)								x†		
Phone call to participant								х	x#	
EQ-5D-5L questionnaires		x							х	х
11-14 week ultrasound scan (if participant becomes pregnant)									х	
Final outcomes (conception failure; pregnancy, antenatal, intrapartum, post- partum, Day 28 neonatal and maternal outcomes)										х

*Exact month determined by when the participant becomes pregnant (e.g. if they become pregnant in month 1, subsequent assessments will be made in month 4). **Exact month determined by when participant becomes pregnant, and if they miscarry or have a successful live birth. †Pregnancy to be confirmed by month 6, visit 2 scheduled accordingly. #Second phone call to be made at week 15 of pregnancy.

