# 4. ELIGIBILITY

## 4.1. Inclusion Criteria

Women diagnosed with PCOS (according to Rotterdam criteria) and evidence of anovulation (anovulation is defined as irregular cycles lasting <21 or more than 35 days or less than 8 periods per year OR absence of raised serum progesterone greater than 20nmol/l 7 days prior to a period);

Presentation with infertility or wishing to conceive;

 LOCI PROTOCOL
 Sponsor's reference: RG\_18-272
 v1.0 07-Nov-2019
 Page 22 of 57

 IRAS ID: 257918
 EudraCT number: 2018-004641-16
 ISRCTN: TBC

- Male partner with normal sperm count (≥ 15 million) and progressive motility (≥ 32%) in the last 3 years;
- Willing and able to give informed consent.

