The results reported in these papers will follow the strategy set out here. Subsequent analyses of a more exploratory nature will not be bound by this strategy, though they are expected to follow the broad principles laid down here. The principles are not intended to curtail exploratory analysis (e.g. to decide cut-points for categorisation of continuous variables), nor to prohibit accepted practices (e.g. transformation of data prior to analysis), but they are intended to establish rules that will be followed, as closely as possible, when analysing and reporting data.

Any deviations from this SAP will be described and justified in the final report or publication of the trial (using a table as shown in Appendix A). The analyses will be carried out by an appropriately qualified statistician, who will ensure integrity of the data during their data validation processes.

2. Background and rationale

The background and rationale for the trial are outlined in detail in the protocol. In brief, infertility affects one in six couples, with 25% of infertility being due to anovulation (not releasing eggs from the ovaries). Polycystic ovary syndrome (PCOS) is also very common (approximately 10% of women of reproductive age in the UK have this condition), and it is responsible for 85% of anovulation. Invasive treatments, such as an operation called ovarian diathermy or in-vitro fertilisation (IVF), may overcome anovulation from PCOS, but are associated with significant risks and costs. An effective oral tablet treatment would reduce the need for invasive, risky and costly fertility treatments for women with PCOS, and may improve patient experience.

Eligibility:

Inclusion criteria:

- Women diagnosed with PCOS (according to Rotterdam criteria) and evidence of anovulation (anovulation is defined as irregular cycles lasting <21 or >35 days, OR fewer than 8 periods per year, OR absence of raised serum progesterone >20 nmol/l seven days prior to a period);
- Presentation with infertility or wishing to conceive;
- Male partner with normal sperm count (\geq 15 million per millilitre (ml)) and progressive

motility \geq 32% OR total motility \geq 40% in the last 3 years;

- Willing and able to give informed consent;
- Age \geq 18 to \leq 42 years at randomisation;
- Body Mass Index \leq 35 kg/m².

Exclusion:

- More than six previous OI (ovulation induction) treatments (cycles) with either letrozole or clomifene in the previous 12 months;

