9.4. Data manipulations

The trial statistician will derive all responses from the raw data recorded in the database:

Other:

• Maternal age at randomisation (years)

(Date of randomisation-date of birth)/365.25.

Outcome Measures:

Primary Outcome

• Live births at and beyond 34 completed weeks of gestation, as a proportion of all women randomised.

CRF: LOCI: 07. Pregnancy Outcome Form **Question:**

AND \circ `Gestation at pregnancy end' = \geq 34 weeks
Exclude participants where: pregnancy outcome is miscarriage, ectopic, still birth or termination and any participants who had a live birth <34 weeks. Participants will be censored if they withdraw or are lost to follow-up before pregnancy end. They will be censored at the point of withdrawal/lost to follow-up. Secondary outcomes
Treatment outcomes:
Number of ovulation induction cycles to live birth
 CRF: LOCI: 04. End of Ovulation Induction/Pregnancy Confirmation Form Question: `Number of completed OI treatment cycles?' `Did the participant become pregnant within 240 days (8 months) of randomisation?' = Yes
CRF: LOCI: 07. Pregnancy Outcome Form Question: • Was the baby born alive? = Yes
No. of women who ovulated
 CRF: LOCI: 03. OI Drug Compliance and Ovulation Tracking Form Question: 'Was an LH surge confirmed?'= Yes OR 'Progesterone concentration' = >20 nmol/l OR USS follicular tracking 'Was ovulation demonstrated?' = Yes
If any of these criteria are fulfilled at any one of the treatment cycles, then this would indicate

• 'Was the baby born alive?' = Yes;

If any of these criteria are fulfilled at any one of the treatment cycles, then this would indicate that ovulation has occurred.

Ovulation rate (total number of ovulations / total number of ovulation induction cycles)

TOTAL NUMBER OF OVULATIONS:

CRF: LOCI: 03. OI Drug Compliance and Ovulation Tracking Form

Question:

• 'Was an LH surge confirmed?'= Yes

OR

• 'Progesterone concentration' = >20 nmol/l

OR

USS follicular tracking

• 'Was ovulation demonstrated?' = Yes

Obtain total number of ovulations by totalling each 03. OI Drug Compliance and Ovulation Tracking Form per cycle where ovulation has occurred.

TOTAL NUMBER OF OVULATION INDUCTION CYCLES

CRF: LOCI: 04. End of Ovulation Induction/Pregnancy Confirmation form **Question:**

• 'Number of completed OI treatment cycles?'

OVULATION RATE = Total number of ovulations / Total number of ovulation induction cycles

• Time from randomisation to pregnancy

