9.5. Analysis methods – primary outcome(s)

A template for reporting the primary outcome will be given in a separate template report.

The primary outcome is the proportion of women randomised who experience a live birth at and beyond 34 weeks of gestation. The denominator of this proportion will be all women randomised and the numerator will be those women who have conceived during the six ovulation induction cycles (maximum 240 days) and have gone on to have a live birth at or beyond 34 weeks.

A mixed effects binomial regression model will be used to calculate the risk difference (identity link) and relative risk (log link) with 95% confidence intervals for the primary outcome (live birth \geq 34 weeks), adjusting for the randomisation variables listed in section 4.6. If this primary method doesn't converge, the plan detailed in section 9.1 will be followed.

Statistical significance of the treatment group parameter will be determined (p-value generated) through examination of the associated chi-squared statistic (this will be obtained from the log-binomial model which produces risk ratios).

Summary data of the primary outcome in the form of frequencies and percentages will be produced that looks at the primary outcome for all the combinations of treatments (combinations A-D as per section 6.2 Baseline characteristics).

In the event of babies from a multiple pregnancy having different pregnancy outcomes, if at least one of the babies had a live birth \geq 34 weeks then this will count as a live birth \geq 34 weeks overall. If all those babies within that multiple pregnancy have the same pregnancy outcome (e.g. all are live births) then this will only be counted as one outcome (event).

See section 9.1 for covariate adjustment and model convergence.

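### SAP 9.4 reads a day-21 progesterone with no timing rule and ignores pregnancy, so a late ovulation may be scored as none and a woman who conceived may count as never having ovulated

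*SAP*

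**What the plan says.** Protocol 8.2 and SAP Appendix C both schedule, in each of months 1 to 6, a "D21 progesterone concentration blood test (where applicable". Neither has a rule for moving or repeating it in a longer cycle. Ultrasound monitoring is left to local practice and, as the table reads, is ticked under month 1 only. LH testing has no row.

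The only progesterone timing rule in either document is in the eligibility definition of anovulation: "absence of raised serum progesterone greater than 20nmol/l 7 days prior to a period" (Protocol 4.1) and "absence of raised serum progesterone >20 nmol/l seven days prior to a period" (SAP section 2).

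SAP 9.4 scores a cycle as ovulatory if any one of three items is positive: "Was an LH surge confirmed?'= Yes OR 'Progesterone concentration' = >20 nmol/l OR USS follicular tracking 'Was ovulation demonstrated?' = Yes". It names no sampling day and does not list pregnancy. The outcome is the "Ovulation rate (total number of ovulations / total number of ovulation induction cycles". The numerator comes from the per-cycle Form 03, and the denominator is the Form 04 count of completed cycles. The number of women who ovulated needs one positive item in any cycle.

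**The concern.** The cut-off used at entry is tied to the next period. The outcome keeps the cut-off and drops the timing. A sample taken before progesterone has risen cannot exceed 20 nmol/l, however normal the cycle. There is no category for a cycle that could not be evaluated, so such a cycle counts as not ovulated unless LH or ultrasound rescues it.

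The clearest symptom is the conception cycle. Conception implies ovulation, yet SAP 9.4 can score that cycle as anovulatory. It has no next period, so the entry wording cannot settle it either.

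At stake are the ovulation rate and the number of women who ovulated. The ovulation judgement also appears in the passages on escalation (treatment details under the Protocol's trial schema; SAP 4.2).

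**Working it through.** **Inputs from the documents.** Sampling on day 21 (Protocol 8.2, SAP Appendix C). Cut-off >20 nmol/l (SAP 9.4). Entry timing of 7 days before a period (Protocol 4.1, SAP section 2). At most 240 days for six cycles (SAP 9.5), counted from randomisation (SAP 9.4). Ovulation induction of up to six months (Protocol 7.1). Seven calendar months of metformin or placebo for the six cycles (Protocol 7.7.2).

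**Assumptions, not in the documents.** A luteal phase of 14 days. Progesterone passes 20 nmol/l 4 days after ovulation (range 3 to 5).

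**Step 1: cycle length implied by the plan.**
- 240 / 6 = 40 days, a ceiling on the average
- six months: 182.6 / 6 = 30.4 days
- seven months: 213.1 / 6 = 35.5 days

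**Step 2: where day 21 falls.** For a cycle of L days, the entry-rule sample is on day L − 7 and ovulation is on day L − 14.

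| L (days) | Entry-rule day | Day 21 early by | Ovulation day | Day 21 relative to ovulation |
|---|---|---|---|---|
| 28 | 21 | 0 | 14 | 7 days after |
| 30.4 | 23.4 | 2.4 | 16.4 | 4.6 days after |
| 35.5 | 28.5 | 7.5 | 21.5 | 0.5 days before |
| 40 | 33 | 12 | 26 | 5 days before |

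**Step 3: latest ovulation that day 21 can detect.** 21 − 4 = day 17 (21 − 3 = 18; 21 − 5 = 16). Adding 14 days, this is a cycle of 31 days (30 to 32). The shortest average in step 1, 30.4 days, lies almost on that limit.

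**Step 4: can the size be pinned down?** Suppose ovulatory cycle length is normal with mean μ and SD 3 to 5 days (assumed). The share of ovulatory cycles with progesterone still too low on day 21 is 1 − Φ((31 − μ)/SD).
- μ = 30.4: 42% to 45% (30% to 55% over lags of 3 to 5 days)
- μ = 35.5: 82% to 93%
- μ = 40: 96% to over 99%

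These shares are before any rescue by LH or ultrasound. If the true rate is t, the share missed by progesterone is m and the fraction of those rescued is c, the recorded rate is t × (1 − m(1 − c)). Take t = 80% and m = 30%:
- c = 0: 0.80 × 0.70 = 56%
- c = 0.5: 0.80 × 0.85 = 68%
- c = 1: 80%

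The documents give none of μ, SD, m or c, overall or by arm. The error can therefore be anything from nil to large.

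**Step 5: the conception cycle.** A woman ovulates on day 20 of her first cycle, has a day-21 progesterone of 20 nmol/l or less and no LH or scan result, and conceives. Her ovulation rate is 0/1 and she is not among the women who ovulated. Her cycle is in the denominator, because SAP 9.4 uses the same Form 04 cycle count for cycles required for pregnancy.

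**Step 6: would excluding mistimed negatives be safe?** Suppose values of 20 nmol/l or less counted only when sampled 4 to 10 days before the next period. On day 21 that means cycles of 25 to 31 days. Assume ovulatory cycles with mean 30 and SD 3, a lag of 4 days, every anovulatory cycle longer than 31 days, no LH or scan result, and true rates of 75% and 60%. The present rule records 0.75 × Φ(1/3) = 0.75 × 0.63 = 47% and 0.60 × 0.63 = 38%, which keeps the direction. The exclusion rule drops every negative cycle and keeps every positive one, so both arms read 100%.

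**The case against.** Several points against the concern stand.

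- **Progesterone is not the sole criterion.** A positive LH or ultrasound result on the per-cycle form also counts. A reader might infer that every late ovulation is lost. The documents support only that it may be lost when neither of these is positive.
- **Forty days is a ceiling.** The window of "conceived during the six ovulation induction cycles (maximum 240 days" runs from randomisation, and other passages imply about 30 to 36 days. The entry wording on cycles over 35 days describes women before treatment, not induced cycles.
- **There is no direct contradiction.** The rule of seven days before a period belongs to eligibility. The outcome names no day, so a later sample above 20 nmol/l would count, and the schedule row allows some latitude. That latitude does not supply a scoring rule for an early sample.
- **The outcome is secondary.** Protocol 13.2 does not test exploratory secondary outcomes, and SAP 5.1 plans p-values for the primary and safety outcomes.
- **The number of women who ovulated is less exposed,** because one positive cycle is enough.
- **The protocol to hand is v1.0 of November 2019.** The SAP records a sample-size revision of February 2023 and different eligibility criteria. Later sampling guidance cannot be excluded.

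A reader might also infer a false difference between letrozole and clomifene. With a true rate of 75% in both arms, mean ovulation on day 16 versus 17, SD 3, a cut-off of day 17.5 and no LH or scan rescue, the recorded rates would differ by 0.75 × [Φ(0.50) − Φ(0.17)] = 0.75 × (0.69 − 0.57) = 9 points. The documents contain nothing on ovulation timing by arm, so this shows only what would follow from an invented shift.

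**Conclusion.** The concern holds in limited form. With progesterone as the only positive-capable marker, ovulation after about day 17 (day 16 to 18) may be recorded as no ovulation. This rests on the assumed lag of 3 to 5 days. That a conception cycle can be scored as not ovulated follows from the SAP 9.4 criteria themselves, which omit pregnancy.

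The size of the error and any imbalance between arms cannot be determined from the documents; the percentages in the working are illustrations. Live birth at 34 weeks or later is not derived from ovulation status, so the primary analysis and its power are untouched. The matter deserves correction because ovulation rate is reported with an estimate and confidence interval, and one part of the error can be removed with data already collected.

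**What to change.** 1. In SAP 9.4, count a cycle that ends in a positive pregnancy test as ovulated, for both the ovulation rate and the number of women who ovulated. Form 04 already holds the pregnancy answer and test date. The cost is one line of derivation and a rule linking the test date to the cycle.
2. Otherwise keep the present derivation as the main analysis. Where sample and next-period dates exist, add a sensitivity analysis that scores mistimed results of 20 nmol/l or less first all as not ovulated, then all as ovulated. Report their number by arm. Do not simply drop them: excluding long cycles depends on the outcome and, as step 6 shows, can erase a real difference.
3. Reconcile the day-21 schedule row with the entry wording on seven days before a period, and with the passages that make escalation depend on ovulation. No clinical rule is proposed here.

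The downside is a little more programming. The bounds may be wide, and they need dates whose collection is assumed. If the dates were not collected, state the limitation in the report.
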